6.4. Screen Failures

Individuals who do not meet the criteria for participation in this study (screen failure) may be re-screened one additional time. If re-screening is performed, the individual must sign a new ICF and be assigned a new identification number.

If laboratory tests are repeated during the screening period, this does not constitute re-screening.

7. Treatment

The investigator or his/her designee is responsible for the following:

- explaining the correct use of the drugs and planned duration of each individual's treatment to the study site personnel
- verifying that instructions are followed properly
- maintaining accurate records of study drug dispensing and collection
- returning all unused medication to Lilly, or its designee, at the end of the study, unless the site is authorized by Lilly to destroy unused medication, as allowed by local law.

7.1. Treatment Administered

7.1.1. Dose Escalation (Phase 1a)

In the monotherapy dose escalation (Phase 1a), approximately 30-64 patients will start with a starting dose of LY3405105 1 mg PO QD (Part A1) on a 28-day cycle. The dose escalation method is described in Section 7.1.1.2.

Safety data, in particular AEs, will be the primary criteria for the dose escalation. In addition, if available at the time of dose escalation decision, PK and PD results will be used for dose escalation. No dose escalation can occur without prior discussion and agreement between Lilly and the investigators.

7.1.1.1. Dose-Limiting Toxicity Determination and Maximum Tolerated Dose Definition

Dose-limiting toxicity is defined as a clinically significant AE during Cycle 1 of the dose escalation phase that is possibly related to LY3405105 during Phase 1a and fulfills any one of the following criteria using the National Cancer Institute's Common Terminology Criteria for Adverse Events (CTCAE) v4.0:

- \geq CTCAE Grade 3 non-hematological toxicity. Exceptions will be made for:
 - Grade 3 nausea or constipation that lasts for <72 hours and can be controlled with treatment
 - Grade 3 diarrhea, vomiting, or electrolyte disturbance that lasts for <72 hours and can be controlled with treatment
 - fatigue or anorexia. Grade 3 or Grade 4 fatigue should be considered a DLT if persisting >5 days
 - Transient Grade 3 elevations of alanine aminotransferase (ALT) and/or aspartate aminotransferase (AST), without evidence of other hepatic injury, in the setting of preexisting hepatic metastasis and baseline elevation of these values may not be considered a DLT if agreed by the study investigator and Lilly CRP/CRS.

- Total bilirubin $>2 \times$ upper limit of normal (ULN) with ALT/AST $>3 \times$ ULN in the absence of cholestasis (alkaline phosphatase $<2 \times$ ULN)
- Grade 4 neutropenia >5 days duration
- any febrile neutropenia
- Grade 4 thrombocytopenia of any duration
- Grade 3 thrombocytopenia with clinically significant bleeding
- Grade 3/4 anemia
- any other significant toxicity deemed by the primary investigator and Lilly to be dose limiting (for example, any toxicity that is possibly related to the study medication that requires the withdrawal of the patient from the study during Cycle 1 or certain Grade 2 AEs affecting vital organs)
 - A DLT-equivalent toxicity is defined as an AE occurring after Cycle 1 for a patient enrolled in Phase 1a. It will also apply to patients treated in any cycle in Phase 1b (including Cycle 1) that would have met the criteria for DLT.

Potential DLTs that are AEs which are reasonably anticipated AEs for concomitant medication should be reviewed by the treating investigator and Lilly before final determination as a DLT. Review and discussion may include additional participating investigators. Such review may determine that confounding factors render the case to be not evaluable for the purposes of dose selection. For the purpose of this study, the MTD is defined as the highest tested dose that has less than 33% probability of causing a DLT.

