7.1.2. Dose Expansion (Phase 1b)

After the monotherapy RP2D has been determined from Phase 1a, approximately 20 patients will be enrolled in each of Phase 1b Cohorts 1-4. In Cohort 5, approximately 30 patients will be enrolled. Patients will receive LY3405105 at the RP2D orally daily for a 28-day cycle.

Study treatment should be continued until evidence of disease progression or discontinuation criteria is met. Patients with documented progressive disease may be allowed to continue LY3405105 if the patient is tolerating treatment and, in the opinion of the investigator, is deriving clinical benefit from continuing study treatment and continuation of treatment is approved by the Sponsor.

If DLT-equivalent toxicities occur in 33% or more of patients within a tumor-specific cohort expansion, then investigators and the Lilly CRP/CRS will assess the nature and severity of these toxicities. If a treatment-related death or Grade 4 toxicity not clearly due to underlying disease or extraneous occur, then the investigators and the Lilly CRP/CRS will assess the nature and severity of the toxicities and whether the trial should be stopped due to unacceptable toxicity. No additional patients will be accrued until this safety review is completed and a decision is made either to continue at the current dose or to de-escalate the dose and define a new dose for the expansion phase. The safety review and decision will be documented in writing.

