Hematologic toxicity: Patient requires administration of blood cell growth factors	Regardless of severity. Growth factors use according to ASCO guidelines	Dose MUST be suspended for at least 48 hours after the last dose of blood cell growth factors was administered and until toxicity resolves to at least Grade 2.	Dose MUST be reduced by 1 dose level unless already performed for incidence of toxicity that lead to the use of growth factor.
Nonhematologic toxicity (except diarrhea)	Persistent or recurrent Grade 2 that does not resolve with maximal supportive measures within 7 days to baseline or Grade 1	Dose MAY be suspended until toxicity resolves to either baseline or Grade 1.	Dose MAY be reduced by 1 dose level – investigator's discretion.
Nonhematologic toxicity	Grade 3 or 4 that does not resolve with maximal supportive measures within 72 hours to baseline or Grade 1	Dose MUST be suspended until toxicity resolves to either baseline or Grade 1.	Dose MUST be reduced by 1 dose level.
Diarrhea	Requires hospitalization for Grade 3 or 4	Dose MUST be suspended until toxicity resolves to at least Grade 1.	Dose MUST be reduced by 1 dose level.
Diarrhea	Persistent or recurrent Grade 2 that does not resolve with maximal supportive measures within 24 hours to at least Grade 1	Dose MUST be suspended until toxicity resolves to at least Grade 1.	Dose MAY be reduced by 1 dose level – investigator's discretion.
Diarrhea	Persistent or recurrent Grade 1 that does not resolve with maximal supportive measures within 24 hours to baseline	Patient to be followed for 48 hours to ensure grade does not worsen.	Dose MAY be maintained during monitoring – investigator's discretion.
Diarrhea	Diarrhea recurs despite maximal supportive measures after resuming same dose level after initial Grade 2 diarrhea	Dose MUST be suspended until toxicity resolves to at least Grade 1.	Dose MUST be reduced by 1 dose level.
Bloody diarrhea	Any grade	Dose MUST be suspended until bloody diarrhea resolves and diarrhea resolves to at least Grade 1.	Dose MUST be reduced by 1 dose level.
Nonhematologic toxicity (laboratory)	Total bilirubin $>2 \times$ ULN with ALT/AST $>3 \times$ ULN in the absence of cholestasis	Dose MUST be permanently suspended.	Dose MUST be permanently suspended.

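### Anorexia is the only non-hematological DLT exception with no limit, so persistent Grade 3-4 anorexia counts only if the investigator and sponsor choose to count it

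*Protocol*

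**What the plan says.** Protocol 7.1.1.1 defines a DLT as a clinically significant, possibly drug-related adverse event in Cycle 1 of Phase 1a that meets a listed criterion. The first criterion is non-hematological toxicity of Grade 3 or higher, with exceptions. The exception at issue is "fatigue or anorexia. Grade 3 or Grade 4 fatigue should be considered a DLT if persisting >5 days".

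The last criterion is open-ended: "any other significant toxicity deemed by the primary investigator and Lilly to be dose limiting". One of its named examples is "any toxicity that is possibly related to the study medication that requires the withdrawal of the patient from the study during Cycle 1".

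The same section carries the criteria into the expansion phase as DLT-equivalent toxicities: "It will also apply to patients treated in any cycle in Phase 1b (including Cycle 1) that would have met the criteria for DLT". The SAP counts DLTs and DLT-equivalents but does not redefine them.

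The counts are used in four places:
- the N-CRM limit on dose (Protocol 7.1.1.2 and Appendix 7);
- the Phase 1b cohort rule in Protocol 7.1.2, "If DLT-equivalent toxicities occur in 33% or more of patients within a tumor-specific cohort expansion";
- the 7-of-20 pause rule (Protocol 10.3.4);
- the Bayesian toxicity table (SAP 6.12).

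**The concern.** The exception names two symptoms and the sentence that limits it names one. Read literally, possibly drug-related Grade 3 or 4 anorexia lasting all of Cycle 1 is not automatically a DLT. If the patient stays on study, for instance after a suspension or at a reduced dose, the N-CRM can receive that patient as evaluable and DLT-free. In Phase 1b the same event can go uncounted as a DLT-equivalent.

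At stake is consistent counting. Two patients with the same persistent event could be classified differently, depending on whether the investigator and sponsor invoke the last criterion. Any such undercount lowers the estimated DLT rate and never raises it.

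**Working it through.** **1. The exceptions side by side (Protocol 7.1.1.1)**

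| Exception | Grade limit | Duration limit | Other condition |
|---|---|---|---|
| Nausea, constipation | Grade 3 | <72 hours | controllable with treatment |
| Diarrhea, vomiting, electrolyte disturbance | Grade 3 | <72 hours | controllable with treatment |
| Fatigue | none | DLT again if Grade 3-4 lasts >5 days | none |
| ALT/AST elevation | Grade 3 | transient | liver metastasis, raised baseline, no other hepatic injury, investigator and sponsor agree |
| Anorexia | none | none | none |

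Anorexia is the only row with no limit. No other listed criterion captures it except the discretionary last one.

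**2. Which patients are left in the gap**

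- Phase 1a, withdrawn in Cycle 1 for the event: a named example under the last criterion, so largely covered.
- Phase 1a, staying on study: not covered by that example. Protocol 7.6.1 makes a noncompliant patient non-evaluable only when the cause is something other than drug-related toxicity. A patient whose doses were held for anorexia can therefore remain in the denominator as a non-event.
- Phase 1b, Grade 4: Protocol 7.1.2 already requires review, "If a treatment-related death or Grade 4 toxicity not clearly due to underlying disease or extraneous occur". The gap there is mainly persistent Grade 3.

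**3. What one uncounted event does in Phase 1a (illustration on assumed data)**

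The plan gives no figure that depends on this point. The inputs are the example prior in Appendix 7 and the example doses in Table JZFA.7.1. The model is logit p(d) = a + exp(b) × log(d / 1 mg), with (a, b) bivariate normal, means -3.88 and -0.11, SDs 2.85 and 0.17, correlation -0.88. These parameters give prior median DLT rates of 0.020 at 1 mg and 0.306 at 30 mg, where Appendix 7 states 0.01 and 0.28. The results are therefore illustrative only. The limit is P(DLT rate >0.33) <25%. The posterior comes from importance sampling with 4,000,000 prior draws.

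P(DLT rate at 30 mg >0.33), by assumed numbers of DLT-free patients at 1/2/4/8 mg and assumed DLTs at 15 mg:

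| Patients at 1/2/4/8 mg | 0/6 | 1/6 | 2/6 | 0/3 | 1/3 |
|---|---|---|---|---|---|
| 3/3/3/3 | 0.019 | 0.142 | 0.399 | 0.041 | 0.260 |
| 4/4/4/4 | 0.013 | 0.108 | 0.328 | 0.029 | 0.199 |
| 3/3/3/6 | 0.012 | 0.096 | 0.302 | 0.025 | 0.178 |
| 3/3/6/6 | 0.009 | 0.077 | 0.255 | 0.019 | 0.142 |
| 6/6/6/6 | 0.007 | 0.064 | 0.219 | 0.015 | 0.118 |

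- Second event (2/6 recorded as 1/6): the 25% limit is crossed in four of five patterns with 2/6, once marginally (0.255), and in none with 1/6.
- Lone event among six (1/6 recorded as 0/6): 30 mg stays allowed in all five patterns either way.
- Lone event among three (1/3 recorded as 0/3): the limit is crossed in one pattern, marginally (0.260).
- With 2/6, 25 mg stays allowed in four of five patterns (0.148-0.244; the exception is 0.312) and 20 mg in all five (at most 0.217).
- P(DLT rate at 30 mg >0.60) is at most 0.022 throughout, under the 5% limit.

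**4. What one uncounted event does in Phase 1b**

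SAP 6.12 uses a beta(0.5, 0.5) prior, so the posterior is beta(0.5 + x, 0.5 + n - x). The criterion is P(theta >0.3) ≥0.7.

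| n | Printed pause count | P at that count | P with one fewer |
|---|---|---|---|
| 5 | 2 | 0.703 | 0.337 |
| 10 | 4 | 0.762 | 0.519 |
| 15 | 6 | 0.804 | 0.624 |
| 20 | 7 | 0.696 | 0.513 |

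At 7/20 the printed count is met although 0.696 is just under 0.7; 8/20 gives 0.836. Under the 33% cohort rule, 7/20 = 35% becomes 6/20 = 30%, and 10/30 = 33.3% becomes 9/30 = 30%.

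The calculations in steps 3 and 4 apply to any uncounted event. They say nothing about how often anorexia would be that event.

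**The case against.** The strongest reply is that the event is never hidden and can be declared a DLT at any time. The last criterion in 7.1.1.1 allows it. The sponsor and investigators take every escalation decision, and "Safety data, in particular AEs, will be the primary criteria for the dose escalation". The N-CRM sets a ceiling and does not dictate the dose. Protocol 10.3.2 bases the RP2D on all DLTs, TEAEs, PK and PD data. The Phase 1b rules prompt an assessment or a possible pause, not an automatic stop. All of this stands and limits the harm. It does not make the counting consistent, because the last criterion works case by case and an express exemption may discourage its use.

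A reader might infer that Table JZFA.7.2 proves an error, since it requires a one-level reduction for nonhematologic toxicity of "Grade 3 or 4 that does not resolve with maximal supportive measures within 72 hours to baseline or Grade 1" and makes no exception for anorexia. The documents do not support that inference. The protocol requires reductions for other events that are not automatic DLTs, such as Grade 4 neutropenia of 5 days or less, or Grade 3-4 fatigue lasting between 72 hours and 5 days. Dose modification protects the individual patient, whereas a DLT informs whether the dose is tolerable. The table is context only.

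It is also fair that the documents do not show whether leaving anorexia out of the limiting sentence was a slip or a choice, and that the illustrations rest on assumed data.

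**Conclusion.** The gap in the definition is real. As written, persistent, possibly drug-related Grade 3-4 anorexia in a patient who stays on study is a DLT only by discretion. In Phase 1b the same holds for DLT-equivalents, mainly at Grade 3.

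Its practical size is unknown, since neither document reports an anorexia event or an expected rate. Under the assumed cohorts and the Appendix 7 example prior, one uncounted event changes the 30 mg decision mainly when another DLT is already present at 15 mg; a lone event does so in one of ten runs, marginally.

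Two stronger readings should be resisted. Anorexia is not barred from being a DLT, because the last criterion remains available. Nor is the escalation or the RP2D shown to be unsound, because these events are seen in every review. This is a cheap improvement, not a flaw that undermines the design.

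**What to change.** In the second sentence of the exception, insert *or anorexia* after *fatigue*, so that both symptoms become DLTs at Grade 3 or 4 when they last more than 5 days. Apply this prospectively; the DLT-equivalent definition then follows. If the open exemption was intended, state the reason and set a limit.

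For Phase 1a patients already treated, list any possibly related Grade 3-4 anorexia lasting more than 5 days in Cycle 1 that was exempted. If there is any, report an N-CRM sensitivity run beside the recorded result. Do not reclassify DLTs after the data are known, particularly in an open-label study.

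The cost is a two-word amendment to the DLT definition and one query of existing adverse event data. Escalation has already started, so the amendment should state the date from which it applies. The downside is possibly a few more DLTs and slightly slower escalation. Grade 3-4 anorexia lasting between 72 hours and 5 days would still require a reduction without being an automatic DLT, exactly as fatigue does now.

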7.1.1.2. Dose Escalation Method

In the dose escalation part of the study, data will be evaluated on an ongoing basis until the MTD is determined. The Bayesian model-based toxicity band method (N-CRM) (Neuenschwander et al. 2008) that incorporates prior expectations about the dose-toxicity relationship will be fitted to the data at the end of each dose level to recommend a dose for the next dose level. The recommendation is based on the model-based posterior probability of a DLT at each dose and the overdose control criteria. Details regarding the toxicity band model and design are provided in [Appendix 7](#).

During the escalation, the investigators and Lilly will consider both the Bayesian model-based toxicity band method (N-CRM) recommendation and the observed DLT rate at each dose level to determine the next dose level and determine when to stop the escalation.

Dose levels will not exceed those recommended by the toxicity band model. Dose escalation will take into account all available PK and PD information. Additional patients may therefore be enrolled at a specific dose level to better characterize PK/PD.

The starting dose of LY3405105 will be 1 mg QD in Part A1. If the starting dose exceeds the MTD, a lower LY3405105 dose level may be explored. The maximum increment of escalation will be no more than 100%. Each dose level will have a minimum of 3 patients enrolled to it.

Subsequent dose levels will enroll patients based on the safety from the previous dose level, any available PK and PD data, and discussion with investigators. This decision is made between the investigators and the Lilly CRP/CRS. [Table JZFA.7.1](#) shows example dose levels for LY3405105. It should be noted that although an example escalation table is shown below, alternate doses may be selected.

Intermediate, alternate, or higher dose levels will be explored if deemed necessary after discussion between Lilly and the investigators. The toxicity band model accommodates such additional dose levels naturally.

Table JZFA.7.1. Example Dose Escalation Scheme for Study J1F-MC-JZFAa

Dose Level	LY3405105 Part A1 Dose
1	1 mg QD
2	2 mg QD
3	4 mg QD
4	8 mg QD
5	15 mg QD
6	30 mg QD
7	45 mg QD

Abbreviations: QD = once daily.

a Dose levels will start at 1 mg QD (Part A1) and maximum increase will be no more than 100% from previous level. Table lists example dose levels which may be used.

7.1.2. Dose Expansion (Phase 1b)

After the monotherapy RP2D has been determined from Phase 1a, approximately 20 patients will be enrolled in each of Phase 1b Cohorts 1-4. In Cohort 5, approximately 30 patients will be enrolled. Patients will receive LY3405105 at the RP2D orally daily for a 28-day cycle.

Study treatment should be continued until evidence of disease progression or discontinuation criteria is met. Patients with documented progressive disease may be allowed to continue LY3405105 if the patient is tolerating treatment and, in the opinion of the investigator, is deriving clinical benefit from continuing study treatment and continuation of treatment is approved by the Sponsor.

If DLT-equivalent toxicities occur in 33% or more of patients within a tumor-specific cohort expansion, then investigators and the Lilly CRP/CRS will assess the nature and severity of these toxicities. If a treatment-related death or Grade 4 toxicity not clearly due to underlying disease or extraneous occur, then the investigators and the Lilly CRP/CRS will assess the nature and severity of the toxicities and whether the trial should be stopped due to unacceptable toxicity. No additional patients will be accrued until this safety review is completed and a decision is made either to continue at the current dose or to de-escalate the dose and define a new dose for the expansion phase. The safety review and decision will be documented in writing.

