10.3.3.6. Biomarker Analyses

Biomarkers related to treatment, immune response, mechanism of action, and/or cancer will be measured and analyzed. The association of biomarker and clinical outcome will be assessed via single-marker and/or multi-marker analysis.

10.3.4. *Interim Analyses*

Because this is a dose-finding study, data will be reviewed on a dose level-by-dose level basis during the dose escalation, until the MTDs are determined. The purpose of these dose level-by-dose level reviews is to evaluate the safety data at each dose level and determine if a DLT has been observed that would suggest MTD has been met or exceeded. The investigators and the Lilly study team will make the determination regarding dose escalation based upon their review of the safety and tolerability data (and PK/PD data were available) as described in this protocol.

For Phase 1a, after all patients who are deemed evaluable for the assessment of dose levels complete DLT evaluation period or MTD is determined, an interim analysis for safety and PK will be conducted.

For Phase 1b, a safety review will be performed after the first 20 patients across all cohorts are enrolled and treated for 1 cycle, and then every 6 months afterward. The purpose of this safety review is to evaluate the safety and tolerability for each expansion cohort and determine if a dose-limiting equivalent toxicity (DLET) has been observed. For the first 20 patients enrolled into Phase 1b, if in 7 patients or more DLETs are observed, accrual may be temporarily paused, and the available data from Phase 1a and Phase 1b will be analyzed to potentially modify the RP2D, or the study. Considerations for stopping recruitment should be given after discussion with the investigator and the Sponsor.

Continued monitoring for safety and efficacy will occur in Phase 1b and if aggregate data suggest that continued enrollment is unlikely to alter the outcome or present an unreasonable risk to patients, enrollment into any one or all Cohorts 1-5 may be stopped.

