Bayesian Toxicity Monitoring Plan (U-Design [WWW], version 1.3): Assuming the maximum permissible probability of toxicity is 0.3, the probability threshold for declaring excessive toxicity is 0.7, we may stop the trial if the posterior probability $P(\theta > 0.3|n, x) \geq 0.7$, where θ is the true toxicity rate, n is the current number of patients, and x is the number of DLETs. A precalculated decision table by posterior probability of toxicity (assuming a beta(0.5, 0.5) prior) is shown in [Figure JZFA.6.1](#). From the precalculated table, if the number of patients with DLETs observed among 5, 10, 15, and 20 treated patients is greater or equal to 2 (40%), 4 (40%), 6 (40%), and 7 (35%), respectively, based on the totality of data, accrual may be paused and the available data from Phase 1a and Phase 1b will be analyzed to potentially modify the RP2D or the study.

Table TM: Decision Table by Posterior Probability of Toxicity

Notes:

1.red denotes the posterior probability of toxicity $Pr(\theta > \theta_{max} | Data)$ is larger than $\theta_T = 0.7$.

2.green on the opposite.

Figure JZFA.6.1. Bayesian toxicity monitoring decision table.

If it is deemed that enough data are obtained to assess the primary objective and the secondary objectives, a CSR might be created before the last patient visit. In this case, all data until the data-cutoff date will be used for the analysis of safety, efficacy, PK, and PD biomarkers. All data defined in the protocol will continue to be collected from patients on treatment after the data-cutoff date. These data may be reported separately and the analyses on all patients including these data may not be performed.

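### Phase 1b has two families of toxicity-hold rule that are not reconciled with each other, and the SAP's 7-of-20 boundary misses the SAP's own posterior criterion.

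*Protocol*

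**What the plan says.** **Protocol 7.1.2 (Dose Expansion).** The first trigger applies "If DLT-equivalent toxicities occur in 33% or more of patients within a tumor-specific cohort expansion". The investigators and the sponsor physician then assess the nature and severity of the toxicities. No minimum number of patients is given. A second trigger follows: "If a treatment-related death or Grade 4 toxicity not clearly due to underlying disease or extraneous occur", the toxicities are assessed, together with whether the trial should stop. The paragraph then adds: "No additional patients will be accrued until this safety review is completed and a decision is made either to continue at the current dose"; the alternative it names is a lower dose.

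**Protocol 10.3.4 (Interim Analyses).** In the expansion phase, "a safety review will be performed after the first 20 patients across all cohorts are enrolled and treated for 1 cycle"; further reviews come every 6 months. Among those first 20, "if in 7 patients or more DLETs are observed, accrual may be temporarily paused". SAP 6.12 repeats this rule.

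**SAP 6.12, Bayesian toxicity monitoring plan.** The trial may be stopped if P(θ > 0.3 | n, x) ≥ 0.7 under a beta(0.5, 0.5) prior, where x counts dose-limiting equivalent toxicities (DLETs). The boundaries are then listed by count: "if the number of patients with DLETs observed among 5, 10, 15, and 20 treated patients" reaches 2, 4, 6 and 7 respectively, accrual may be paused, based on the totality of data. The text does not say whether n is pooled or per cohort.

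**Protocol 7.1.1.1.** In Phase 1b, DLT-equivalent toxicities count from any cycle.

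**The concern.** These rules protect Phase 1b patients and can lead to a change in the dose used in expansion. They differ in three respects:

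- **Unit:** one tumor cohort, all cohorts pooled, or not stated.
- **Looks:** no set look or minimum n, one numeric look at 20, or looks at 5, 10, 15 and 20. The looks at 5, 10 and 15 are not in the protocol.
- **Force:** no further accrual until review, against a pause that may be made. The SAP paragraph itself speaks both of possibly stopping the trial and of possibly pausing accrual at the same boundary.

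No passage says which rule governs, or that they act together. The chance of crossing a boundary when the true rate is acceptable cannot be stated until this is settled. In addition, a boundary printed in both documents does not satisfy the criterion from which the SAP says it was calculated.

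**Working it through.** **1. Reproduce the SAP boundaries.** Inputs from SAP 6.12: limit 0.3, threshold 0.7, prior beta(0.5, 0.5). With x DLETs in n patients, the posterior is Beta(0.5 + x, 0.5 + n − x), and the tail is 1 − F(0.3).

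| x/n | Posterior | P(θ > 0.3) | ≥ 0.7? |
|---|---|---|---|
| 2/5 | Beta(2.5, 3.5) | 0.703 | yes |
| 4/10 | Beta(4.5, 6.5) | 0.762 | yes |
| 6/15 | Beta(6.5, 9.5) | 0.804 | yes |
| 7/20 | Beta(7.5, 13.5) | 0.6955 | no |
| 8/20 | Beta(8.5, 12.5) | 0.836 | yes |

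Three of the four boundaries reproduce. By the stated formula, the smallest count at n=20 is 8. A beta(1, 1) prior would give 0.723 at 7/20 and all four printed boundaries, but it is not the stated prior.

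**2. Compare the two families.** The 33% rule needs the smallest integer at or above 0.33n.

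| n | 33% rule | SAP as printed |
|---|---|---|
| 5 | 2 | 2 |
| 10 | 4 | 4 |
| 15 | 5 | 6 |
| 20 | 7 | 7 |

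The counts agree at 5, 10 and 20 when the unit is the same. They part in these cases:

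- **5/15 in one cohort:** 33.3%, so 7.1.2 is met. Even read per cohort, the SAP boundary is not: Beta(5.5, 10.5) gives 0.624, and 6 are needed.
- **2/5 in one cohort and 0/15 in the others:** 40% in that cohort, so 7.1.2 is met. Pooled, it is 2/20 against 7/20.
- **1/3 in one cohort:** 33.3%, so 7.1.2 is met. The SAP has no look at n=3.

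**3. Chance of crossing a boundary.** These are exact binomial results with independent patients and a constant true DLET rate p.

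- **Single look at 20:** P(X ≥ 7) = 8.7% at p = 0.20 and 39.2% at p = 0.30. With 8 as the boundary, P(X ≥ 8) = 3.2% and 22.8%.
- **Four SAP looks, read as pooled (2/5, 4/10, 6/15, 7/20):** carry forward the distribution of counts that have not crossed at each look and sum the mass that crosses. This gives 31% at p = 0.20 and 62% at p = 0.30.
- **33% rule in one 20-patient cohort:** the same recursion patient by patient, with boundary ⌈0.33n⌉. The documents do not say when the rule is tested, so the result is a range:

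| Tested | p = 0.20 | p = 0.30 |
|---|---|---|
| at every n | 59% | 82% |
| from n=5 | 43% | 73% |
| from n=10 | 25% | 61% |
| at n=20 only | 8.7% | 39.2% |

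The last row equals the single 7/20 look because ⌈0.33 × 20⌉ = ⌈6.6⌉ = 7.

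**The case against.** The strongest reply is that a cohort rule and a pooled rule are ordinary layers. A reader might infer that the passages are flatly incompatible. The documents do not support that: no passage forbids a hold that another requires, and acting on whichever trigger is met first breaches none of them. That part of the objection stands. What remains is that neither document says the rules are layers, and the prescribed accrual action differs.

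A reader might also count three separate rules. There are two families, because 7/20 in Protocol 10.3.4 is also the n=20 entry of the SAP table.

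A reader might take the hold at 33% as plainly mandatory. The 33% sentence itself requires only assessment, and the accrual sentence directly follows the death/Grade 4 trigger. The paragraph reads naturally as covering both. If it does not, the 33% trigger has no stated accrual consequence, which also needs saying.

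Other safeguards exist. The 33% rule has no cut-off at 20 patients, Protocol 10.3.4 provides 6-monthly reviews and continued monitoring after that, and investigators and sponsor share the assessment. Counting DLETs from any cycle while the first review waits for one cycle can be read as minimum follow-up, not a contradiction.

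The shortfall at 7/20 is 0.70 − 0.6955 = 0.0045, rounds to 0.70, and errs toward an earlier pause. It is small on the posterior scale, but whether the boundary is 7 or 8 changes the single-look crossing probability from 8.7% to 3.2% at a 20% true rate.

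**Conclusion.** The point holds as a failure to reconcile, together with one boundary that fails its own criterion. The same DLET data can call for an accrual hold under Protocol 7.1.2 (on its natural reading) and for none under Protocol 10.3.4 or SAP 6.12. The 7/20 boundary has a posterior of 0.6955 against a required 0.70, and the stated formula gives 8/20.

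At a true DLET rate of 20%, the chance of crossing runs from 8.7% to 59% depending on the passage followed and how it is read. These are probabilities of meeting a trigger, not of a hold, since the pooled pause is discretionary. The 31% assumes that the SAP looks are pooled. The 59% assumes testing after every patient, so a reader should not infer from it that a hold in some cohort is close to certain: the protocol does not specify such testing, and the figure falls to 25% from n=10. None of these figures includes the death/Grade 4 trigger, for which the documents give no rate. The SAP's decision-table figure is not shown, so only the boundaries printed in the text were checked.

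**What to change.** Reconcile Protocol 7.1.2, Protocol 10.3.4 and SAP 6.12 so that both documents state the same things:

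- the looks, and the unit (cohort or pooled) for each boundary;
- which patients and which event window are counted;
- whether the 33% review carries an accrual hold, and whether each hold is mandatory or discretionary;
- how the cohort, pooled and death/Grade 4 triggers act together, including precedence.

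Make the n=20 boundary agree with the stated prior and threshold. Then print the crossing probabilities of the reconciled rule over a range of true DLET rates. Which rule and which threshold apply is for the sponsor to decide.

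The cost is wording in two documents and one recalculated table, with no added patients or procedures.
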